6. REGIMEN

6.1 Patient pathway – Assessments

- Participants will receive a clinical assessment from their usual managing clinician as part of their usual outpatient appointment. This will involve a physical examination and routine clinical questions.
- A blinded assessor (for example, Trainee, Clinical Fellow, Specialist Nurse) will then examine the patient and record clinical diagnostic features on the CRF. A third assessor who is also blinded may also examine the patient at the Nottingham site. Participants can opt out of examination by two different professionals if they wish, but to participate in SHELLS they must agree to at least one additional examination.
- The blinded assessor will be asked to examine the patient without speaking to the managing clinician. The managing clinician will ensure that the clinical notes are closed

and unable to be viewed by the blinded assessor as they come in the room, and REDCap (Research Electronic Data Capture) will disable access to the clinician diagnosis by the blinded assessor. The patient will be advised not to give any information to the blinded assessor/s other than specific questions that are asked in relation to the research.

- The blinded assessment will ideally take place immediately after the managing clinician has examined the patient. This will prevent disruption of flow to patients coming through the clinic and it will prevent patients from having to get undressed twice.
 - However, we acknowledge that flexibility is required and each site may need to adapt their own flow for how the clinical assessments are performed, ensuring blinding of the additional assessor/s.
- Information collected by the research team (not the blinded assessor) for each participant will include:
 - Age
 - Ethnicity
 - Post code (for socioeconomic status)
 - Participant rating of the condition on the day of assessment
 - Physician global assessment of disease severity (assessed and recorded by managing clinician)
 - Symptom duration
 - Diagnosis of LS prior to clinic appointment
 - Previous diagnosis of a vulval condition (Y/N and what diagnosis)
 - Treatments received (Y/N and what treatment)
 - Treatment duration
 - Whether on active treatment at time of recruitment (Y/N)
 - Whether the patient has 'early or late' stage LS (assessed and recorded by managing clinician)
 - Presence or absence of each of the individual diagnostic features (Index test, see section 3.3.1)
 - Clinical photographs (optional for this study, see below)
 - Managing consultant's diagnosis (reference standard)
 - Biopsy taken or not – if so, result of biopsy. N.B. Biopsies will not be taken specifically for study purposes, only in line with national guidance¹⁷.
 - Participants will be approached by their usual care team for clinical photographs as per standard care. Depending on local site arrangements, photographs will be taken either by Medical Photography or by a departmental camera. During the consent process they will be given the option to allow use of their anonymised clinical images for research purposes. It will be explained that this is to aid the future development of a training manual. The decision to allow anonymised clinical photographs to be used for training/research will be entirely voluntary and at the discretion of the patient. It will be made clear that their decision will not affect their care. The clinical photographs of those who consent for research purposes will be uploaded onto the REDCap study database. If a situation arises where sites are unable to upload onto REDCap, the coordinating centre will first support the site remotely to resolve the issue. Should it not be possible to resolve, instruction to send the images securely by email will be given. Any identifiers will be removed from the images and they will be labelled as follows: Patient study number, Date of Image (DDMMYYYY),_Image number. The images on the email trail will be deleted as soon as upload to REDCap is confirmed

[figure not shown]

Figure 1 – Study flow

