Sample size estimate	
A sample size of 370 people (185 people with the outcome LS and 185 non-LS) is needed to target a confidence interval of 0.45-0.55 for the overall outcome proportion of 0.5 and to target a mean absolute error of 0.062 between observed and true outcome probabilities based on up to nine predictor variables.
 
The final recruitment figure of 407 participants includes a 10% increase for missing data

Number of participants	407 participants will be recruited to the study.
Eligibility criteria	
Inclusion criteria:
 
 • Adults (≥ 18 years of age) • Female • New presentation to a specialist clinic (secondary care or community hub) with a vulval skin complaint 
Exclusion criteria:
 
 • Inability to provide informed consent • Patients with surgical alteration of vulval skin as part of gender reaffirming surgery, or patients not born with a vulva • More than 2 weeks since initial consultation in specialist clinic

Description of interventions	
This is an observational study. There are 17 Delphi-agreed LS diagnostic criteria being tested in this study.
 
Patients will have one study visit lasting approximately 30 minutes. The study visit will include 2 clinical examinations for diagnostic assessment. At one centre (Nottingham), there will be a potential third assessment for testing of the inter-observer variability of the diagnostic criteria.
 
The reference standard diagnostic assessment will be undertaken by the patients' managing clinicians.
 
A trained blinded assessor will examine the patient to record the presence or absence of the Delphi-agreed diagnostic criteria.
 
Information will also be collected from the patient including, age, ethnicity, post code (for socioeconomic status), patient rating of the condition on the day of assessment, physician global assessment of severity, symptom duration, diagnosis of LS prior to clinic appointment, previous diagnosis of a vulval condition, treatments received, treatment duration, whether on active treatment at the time of recruitment, treatment length, and clinical assessment of 'early' or 'late' stage LS.
 
Clinical photographs will be taken in line with usual care and participants can opt out of these being used for research purposes if they wish.
 
Skin biopsy will be taken in line with usual care. Histological diagnosis will be recorded if patients have undergone a biopsy.

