1.2 Management and diagnosis of LS

In the UK, multiple specialities manage vulval skin conditions including dermatology, gynaecology, sexual health and primary care. Pathways of care are not well developed and not all UK regions have specialist vulval services. Teaching of vulval disease in undergraduate and postgraduate medicine is limited, leading to lack of awareness amongst the wider medical community. Delay in diagnosis⁴ and unsatisfactory clinical experience¹⁶ are often experienced by patients with LS. Patient involvement into this research development highlighted that misdiagnosis from non-specialists, ill-defined care pathways and social stigma/embarrassment preventing people seeking help are ongoing issues.

The use of biopsy to diagnose LS is controversial, and confirmatory biopsy is not necessary when typical clinical features are present.¹⁷ Histological findings can be varied and non-specific, even in clinically evident LS.¹⁸ This is likely due to sampling error; it is important to biopsy the correct area to give the greatest chance of typical histological features. UK guidelines state that biopsy is indicated if there are atypical features or diagnostic uncertainty; it is essential if there is suspicion of neoplastic change.¹⁷ Biopsy is not a routine procedure in primary care and should only be performed when necessary in secondary care by an experienced operator to minimise false-negative results.

First-line treatment with a super potent topical steroid, in conjunction with simple vulval hygiene measures, brings disease remission in 70% of adult females over a 3-month period.^{11,19} Therefore, early recognition and treatment is important as most patients respond well and progression of disease can be slowed or even halted.

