6.2 Assessors

Each site will have at least one blinded assessor who does not know the managing clinician's diagnosis. The independent assessor will examine the patient to record clinical diagnostic features as soon as possible after the clinician has made their assessment. The blinded assessor can be any individual included in the delegation log who is trained in vulval skin examination, and considered competent to do so by the Principal Investigator at the site. The individual is most likely to be, but not limited to the following groups: trainees, clinical fellows, or specialist nurses working alongside the managing clinician.

The research nurse/research support entering data into REDCap will be blinded to the consultant diagnosis.

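### Specialist-first is the default order, and nothing requires the index assessment to come before the patient is told her diagnosis or has a biopsy

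*Protocol*

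**What the plan says.** Section 6.1 describes the managing clinician's assessment, after which the blinded assessor "will then examine the patient and record clinical diagnostic features on the CRF". On timing it says: "The blinded assessment will ideally take place immediately after the managing clinician has examined the patient". Section 6.2 gives the same order, with the assessor working "as soon as possible after the clinician has made their assessment". The reasons given are practical: clinic flow, and sparing the patient a second undressing.

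The order is a default. Section 6.1 adds that "flexibility is required and each site may need to adapt their own flow for how the clinical assessments are performed", provided the additional assessors remain blinded.

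The safeguards in section 6.1 are that the assessor does not talk to the clinician, the notes are closed, and REDCap hides the diagnosis from the assessor. In addition, "The patient will be advised not to give any information to the blinded assessor/s", with an exception for specific questions asked for the research.

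On biopsy, the Synopsis says: "Skin biopsy will be taken in line with usual care". Section 6.1 collects whether a biopsy was taken and its result, and says nothing about timing relative to the index assessment. Section 1.2 notes that "UK guidelines state that biopsy is indicated if there are atypical features or diagnostic uncertainty".

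Section 5.1 also lets women who want more time have their usual consultation first and return for the research visit within two weeks.

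**The concern.** Every safeguard protects the assessor from learning the diagnosis. None protects the patient's answers. If she has just been told that she has, or does not have, lichen sclerosus (LS), and has heard its typical symptoms described, she may answer the symptom questions differently. Those answers are predictors in the model, and the diagnosis that shaped them is the outcome. This is an incorporation-type bias. In its most worrying direction it would inflate symptom coefficients and the C statistic.

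A biopsy taken before the index assessment raises a second, smaller issue. The site may be visible to the assessor and hint at diagnostic uncertainty, and it could affect how skin items are recorded. By section 1.2, any such effect would concentrate in atypical or uncertain cases.

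The tool is meant for non-specialists and for patients themselves (section 1.3), where no specialist has spoken first. The bootstrapping and the internal-external cross-validation in section 7.1 could not reveal the bias if centres share the default order, because it would sit in all the data alike.

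**Working it through.** The protocol gives no figure for this point, so the main check is a reading of the text.

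1. **Order.** Sections 6.1 and 6.2 agree: specialist first, index assessment second. The word for immediate timing is ideally, and sites have discretion. A reversed order is neither named nor excluded.
2. **Condition on the discretion.** It covers blinding of the assessor only. What the patient knows is not mentioned.
3. **Items exposed.** From the list in section 3.3.1, I class itch, irritation, the two pain/soreness items and response to topical corticosteroids as resting wholly or largely on the patient's account: 5 of 17 (5/17 = 29%). Itch and steroid response are two of the five items rated critical. The classification is mine, not the protocol's.
4. **What the patient instruction covers.** It limits volunteered information. Symptom items are research questions, so they fall within its exception.
5. **Disclosure and biopsy.** The text does not say whether either happens before the same-day index assessment. An assessment made straight after the clinician's examination, before the patient dresses, could precede both, but nothing requires it.
6. **Late-consent route (section 5.1).** Here the usual consultation is complete, up to two weeks earlier, so disclosure, and biopsy where one was done, may well have happened already.

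**Illustration of sensitivity, not an estimate.** Inputs from the protocol are 185 LS and 185 non-LS (section 7.2) and the exit criterion p = 0.157 (section 7.1). Assumed: an item with no true association, a yes-rate b of 50%, 60% or 70% in both groups, and disclosure raising the rate by s in LS women only.

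- p1 = b + s
- OR = [p1/(1 − p1)] / [b/(1 − b)]
- SE = √{[b(1 − b) + p1(1 − p1)]/185}
- Chance of passing p < 0.157 on its own (normal approximation) = 1 − Φ(1.415 − s/SE) + Φ(−1.415 − s/SE)

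Example, b = 0.60 and s = 0.10: OR = (0.70/0.30)/(0.60/0.40) = 1.56; SE = √(0.45/185) = 0.0493; s/SE = 2.03; chance = 0.73.

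| Rise s in LS women | Spurious OR (b = 50% to 70%) | Chance of passing |
|---|---|---|
| 0 points | 1.00 | 16% |
| 5 points | 1.22 to 1.29 | 33% to 37% |
| 10 points | 1.50 to 1.71 | 70% to 79% |
| 15 points | 1.86 to 2.43 | 94% to 98% |

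These are univariable chances. The planned model is multivariable, so the figures show only that a modest shift could matter at this retention threshold.

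**The case against.** Several objections are fair.

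- **The order is not rigid.** A reader might infer that the protocol locks the index test behind a completed consultation. It does not: immediate timing is an ideal, and sites may adapt their flow. What stands against the plan is that this discretion is tied only to blinding the assessor.
- **Carry-over is not shown.** A reader might infer that same-day patients already know their diagnosis when they are asked about symptoms. The text does not say so, and the aim of avoiding a second undressing fits an assessment made before any discussion. The study-flow figure was not visible in the copy I read. This objection limits the point to a possibility.
- **The size cannot be derived.** Suppose true itch rates are 70% in LS and 60% in non-LS (OR 1.56), 10% of LS women switch from no to yes, and 10% of non-LS women switch from yes to no. The observed rates are 0.70 + 0.10 × 0.30 = 0.73 and 0.60 − 0.10 × 0.60 = 0.54, and the OR is (0.73/0.27)/(0.54/0.46) = 2.30. With the LS switch alone it is (0.73/0.27)/(0.60/0.40) = 1.80. All these inputs are assumed, and there is no evident reason why women attending with a vulval complaint would start to deny itch. No such figure should be read as the bias in this study.
- **Biopsy is the weaker limb.** The protocol gives no biopsy rate or timing. Assessors must be trained and judged competent at their site (section 6.2), so it should not be inferred that they would mistake a biopsy site for an erosion or fissure.
- **A pre-visit symptom form would do harm.** Section 3.3.1 defines the index test as all 17 features recorded by a blinded assessor, and section 7.1 plans kappa for the individual criteria. Taking five items away from the assessors would change the test and remove those items from the kappa study. This stands, so the symptom items should stay with the assessor.
- **Some women arrive with a diagnosis.** Section 6.1 records whether LS was diagnosed before the appointment. Sequencing within the visit cannot undo that knowledge.

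**Conclusion.** The point holds in a limited form. The protocol makes specialist-first the default for convenience, blinds the assessor but not the patient's answers, and does not place the index assessment before disclosure or a same-visit biopsy. About five of 17 items are open to influence from the reference diagnosis. Skin items or blinding may also be affected in women biopsied first. How often this happens and how large it would be cannot be obtained from the document. It is most likely on the two-week return route and less certain on the same day.

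This rests on my classification of the five items and on the assumption that some women learn their diagnosis before the index questions are asked. It is a cheap improvement to the sequence, not evidence that the model will be invalid. The statistical analysis plan was not available. It may contain a sensitivity analysis, but it could not supply an order that was never recorded.

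**What to change.** In sections 6.1 and 6.2, state that for same-day participants the blinded assessor completes all 17 items, symptom questions included, after the clinician's examination but before the clinician discusses the diagnosis with the patient and before any biopsy at that visit. Whether to biopsy stays with usual care. Make this a condition of the site flexibility, alongside assessor blinding. The index test and the kappa study are then unchanged.

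Add two CRF fields: had the diagnosis been disclosed before the index assessment, and had a biopsy been taken before it. Repeat the model without participants in whom either had happened. Interpret that analysis with care, because excluding biopsied women also removes atypical or uncertain cases, so a changed result would mix case mix with carry-over.

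The cost is a short pause in the consultation, two CRF fields and one sensitivity analysis, with no extra staff, visit or procedure. Two limits remain: the clinician's history-taking still comes first, and women who consent after their consultation cannot meet the order and are covered only by the recording and the sensitivity analysis.

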Duration of study	
Study duration: 24 months.
 
Participant duration: Participants will be involved in a single appointment that will last approximately 30 minutes.

Methods of analysis	
Descriptive analysis will be used to summarise the study population including age, gender, ethnicity, disease severity and stage, disease duration and treatment(s).
 
There will be a 2-stage analysis plan.
 
Stage 1: Developing a diagnostic prediction model
 
i. Refining the diagnostic prediction model: Multivariable backward logistic regression model with exit criteria.
 
ii. Quantifying the performance of the diagnostic prediction model: A calibration plot will assess how well predictions agree with the observed data. Smoothed calibration curves will be plotted using a loess smoother. All data for model development will be included for use in internal-external cross validation across centres (alongside bootstrapping). Discrimination will be measured using the C statistic.

	
iii. Clinical utility: Thresholds on the calibration plot will be based on clinical utility i.e. what defines high risk and trade-offs between benefits and harms, defined by patients and doctors.
 
Stage 2: Model validation
 
Internal validation to (i) obtain an unbiased estimate of the developed model's predictive performance, and (ii) adjust the developed model for optimisation). Bootstrapping and uniform shrinkage techniques will be used for analysis.
 
Inter-observer variability in the assessment of the diagnostic criteria will be calculated using the Kappa statistic.

--	---

ABBREVIATIONS

CI	Chief Investigator overall
CRF	Case Report Form
GCP	Good Clinical Practice
HRA	Health Research Authority
NCTU	Nottingham Clinical Trials Unit
NHS	National Health Service
NIHR	National Institute of Health and Care Research
LS	Lichen Sclerosus
PI	Principal Investigator at a local centre
PIS	Participant Information Sheet
REC	Research Ethics Committee
REDCap	Research Electronic Data Capture
R&D	Research and Development department
UoN	University of Nottingham

TABLE OF CONTENTS

STUDY PERSONNEL AND CONTACT DETAILS	2
SYNOPSIS	4
ABBREVIATIONS	7
1. STUDY BACKGROUND INFORMATION AND RATIONALE	10
2. STUDY OBJECTIVES AND PURPOSE	11
2.1 Purpose	11
2.2 Primary objective	11
2.3 Secondary objective	11
3. STUDY DESIGN	12
3.1 Study configuration	12
3.2 Setting	12
3.3 Index and reference tests	12
3.3.1 Index test	12
3.3.2 Reference standard	13
3.4 Study flow	13

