1.3 Study rationale

Whilst LS can be treated, it is often difficult to diagnose, especially for non-specialists. There are no specific checklists to guide doctors in what they should be looking for. This means that LS often goes under-recognised and undertreated, with community diagnosis being delayed, preventing the initiation of early effective therapy.²⁰ Patients often self-diagnose thrush and obtain over the counter treatments. Misdiagnosis is also common when patients present to primary care/non-specialists. To aid early diagnosis, patients, primary care providers and health professionals not experienced in this field need a simple method of recognising vulval LS. Effective diagnosis will lead to earlier treatment and when needed, timely referral to specialist care. This will reduce complications such as scarring, anatomical changes and progression to vulval cancer.

A four-round electronic-Delphi consensus study has been undertaken by the University of Nottingham with international expert stakeholders to agree the most important clinical diagnostic criteria for LS (Establishing diagnostic criteria for vulval lichen sclerosis (SHELLS): an international electronic-Delphi consensus study).²¹ The study was approved by the University of Nottingham's Faculty of Medicine & Health Sciences Research Ethics Committee (FMHS 39-0722).

A total of five diagnostic features reached consensus as 'critical' and 12 were rated 'important but not critical'.

The aim of this diagnostic test accuracy study (SHELLS) is to test the Delphi criteria agreed as 'critical', and/or 'important but not critical', in the clinical setting, and subsequently develop a diagnostic tool which will support the diagnosis of LS. The diagnostic tool will be available for use by a range of health professionals (not only skin specialists) to diagnose LS as well as to help patients self-diagnose in the community.

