5.2 Eligibility Criteria

5.2.1 Inclusion criteria

- Female
- ≥18 years of age
- New presentation to a specialist clinic (secondary care or community hub) with a vulval skin complaint

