5.2.2 Exclusion criteria

- Inability to provide informed consent
- Patients with surgical alteration of vulval skin as part of gender reaffirming surgery, or patients not born with a vulva
- More than 2 weeks since initial consultation from managing clinician

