7 ANALYSES

7.1 Methods

[name] will undertake the analysis of the data under the supervision of [name] (Study Statistician).

Demographic data and participant characteristics will be analysed descriptively.

Stage 1

Developing a diagnostic prediction model:

i. Determining a predictive model of diagnostic criteria for vulval LS: All criteria identified will be included in a backward multivariable logistic regression model²² with exit criteria $p=0.157$.²³

ii. Quantifying the performance of the diagnostic prediction model: Explained variation will be measured by Cox-Snell R-squared. A calibration plot will assess how well predictions agree

with the observed data. Smoothed calibration curves will be plotted using a loess smoother.^{24,25} All data for model development will be included for use in internal-external cross validation across centres (alongside bootstrapping). Discrimination will be measured using the C statistic.²⁶ The model will be fitted to this dataset.

iii. Clinical utility: Thresholds on the calibration plot will be based on clinical utility i.e. what defines high risk and trade-offs between benefits and harm, defined by patients and doctors.

Stage 2

Model validation

Internal validation is essential to (i) obtain an unbiased estimate of the developed model's predictive performance, and (ii) adjust (shrink) the developed model for optimisation (if necessary). Bootstrapping and uniform shrinkage techniques will be used for analysis.

Missing data: Missing data is not anticipated as the diagnostic features will be assessed by clinical examination. There will be a 'yes' or 'no' answer recorded in the CRF for each criterion in each patient. Only if a participant declines to continue the examination or declines to be examined by the blinded assessor do we anticipate missing index-reference test data pairs. However, the sample size is increased by 10% to account for a maximum of 10% missing data. This will be monitored and if less than 10% data are missing, recruitment target will be reduced accordingly.

c. Inter-observer variability

The inter-observer reliability for assessing the individual diagnostic criteria on 20 cases and 20 non-cases from one of the sites will be calculated using the Kappa statistic. A value of Kappa >60% will be considered acceptable as 'good' agreement between observers.²⁷ At the site where these data are collected (Nottingham, lead site), there will be two independent assessors.

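### Women who already have an LS diagnosis or are on treatment are pooled with undiagnosed women, and section 7.1 plans no report of model performance in the undiagnosed group the tool is meant for

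*Protocol*

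**What the plan says.** Eligibility (Protocol 5.2.1) asks for an adult female with "New presentation to a specialist clinic (secondary care or community hub) with a vulval skin complaint". That is new to the clinic, not newly diagnosed. Section 5.2.2 has three exclusions: inability to consent, a criterion on surgical alteration or not being born with a vulva, and "More than 2 weeks since initial consultation from managing clinician". None concerns an earlier LS diagnosis or current treatment.

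Such women are expected, because section 6.1 collects "Diagnosis of LS prior to clinic appointment", treatments received and their duration, active treatment at recruitment, and early or late stage as judged by the managing clinician.

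On their use, section 7.1 says: "Demographic data and participant characteristics will be analysed descriptively". The synopsis likewise lists stage and treatments under descriptive analysis and does not name prior LS diagnosis there. The model in 7.1 is one backward logistic regression on the Delphi criteria. Calibration, C statistic, bootstrapping and cross-validation across centres are all described for the whole dataset.

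The purpose is set in section 1.3: "To aid early diagnosis, patients, primary care providers and health professionals not experienced in this field need a simple method of recognising vulval LS".

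**The concern.** The group in which performance is measured is wider than the group for which the tool is justified. A woman who arrives already labelled or treated is not someone in whom LS still has to be recognised, and her signs may differ. By the protocol's own account, early LS can be subtle, scarring with loss of anatomy belongs to established disease and is irreversible (1.1), and first-line treatment brings remission in 70% of adult women over three months (1.2). Treated LS can therefore lose reversible features and keep anatomical change.

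One predictor ties treatment history directly to the model. Response to topical corticosteroids is among the five critical items (3.3.1), yet it cannot be observed in a woman who has never had them. Section 7.1 expects a yes or no for every criterion in every patient.

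At stake is what can be concluded. A good pooled C statistic could owe something to women whose LS was already known, and a reader could not tell how the model does in women whose diagnosis is still open.

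**Working it through.** **1. What is fixed and what is not.** The protocol has no figure for the share of participants already diagnosed or treated, so there is no planned value to reproduce on this point. The sample size is not in dispute: at 370 the margin is 1.96 × √(0.25/370) = 0.051. With the usual regression formula for mean absolute prediction error (not printed in the protocol), ln(error) = −0.508 + 0.259 ln(φ) + 0.504 ln(P) − 0.544 ln(n), φ = 0.5, P = 9 and n = 370 give 0.061, against 0.062 stated.

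**2. One reversible sign (all rates assumed).** Let the sign be present in 80% of untreated LS and 20% of untreated non-LS: odds ratio (0.8/0.2)/(0.2/0.8) = 16. Let a share q of women be treated, with the sign cleared in 70% of them. The 70% is borrowed from the remission figure in 1.2, which is not a clearance rate for any single sign. Prevalence becomes 0.8 × (1 − 0.7q) in LS and, if treated alike, 0.2 × (1 − 0.7q) in non-LS.

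| q | LS | Non-LS if treated alike | OR, only LS treated | Log-OR shrinkage | OR, both treated | Log-OR shrinkage |
|---|---|---|---|---|---|---|
| 10% | 0.744 | 0.186 | 11.6 | 12% | 12.7 | 8% |
| 30% | 0.632 | 0.158 | 6.9 | 30% | 9.2 | 20% |
| 50% | 0.520 | 0.130 | 4.3 | 47% | 7.3 | 29% |

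**3. Four signs in a large-sample logistic simulation (all rates assumed).** Rates for anatomical change, whiteness, itch and steroid response:
- early untreated LS: 0.3, 0.6, 0.8, 0
- diagnosed or treated LS: 0.8, 0.5, 0.5, 0.7
- untreated non-LS: 0.1, 0.2, 0.6, 0
- treated non-LS (30% of non-LS): 0.1, 0.2, 0.5, 0.3

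| Share of LS diagnosed or treated | Weight, anatomy | Weight, itch | Pooled C | C, early untreated | Difference | Mean predicted risk, early untreated LS |
|---|---|---|---|---|---|---|
| 0% | 1.36 | 1.09 | 0.800 | 0.775 | 0.025 | 0.64 |
| 10% | 1.70 | 0.96 | 0.792 | 0.776 | 0.016 | 0.63 |
| 30% | 1.97 | 0.81 | 0.805 | 0.769 | 0.036 | 0.59 |
| 50% | 2.24 | 0.67 | 0.839 | 0.768 | 0.071 | 0.55 |
| 70% | 2.55 | 0.48 | 0.876 | 0.762 | 0.114 | 0.48 |

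In the 0% row steroid response occurs only in non-LS, so its coefficient runs off (−29.35) and helps the pooled C. The 10% row is the fairer starting point.

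The last column is not in itself miscalibration, because the LS share among untreated women also falls: (1 − f)/((1 − f) + 0.7) is 0.50 at f = 30% and 0.30 at f = 70%. To separate the two, average the fitted risk over the eight combinations of anatomy, whiteness and itch in untreated women:
- At 30% (intercept −1.75; weights 1.97, 1.72, 0.81) the mean is 0.594 in LS and 0.345 in non-LS, so 0.5 × 0.594 + 0.5 × 0.345 = 0.47 against 0.50 observed.
- At 70% (intercept −2.16; weights 2.55, 1.63, 0.48) it is 0.3 × 0.483 + 0.7 × 0.248 = 0.32 against 0.30.

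The average error is modest. The larger changes are in the weights and in the pooled C.

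**4. What a restricted group would hold.** From 185 LS and 185 non-LS, with the error formula above and P = 9:
- removing 10% of LS only leaves 352 (error 0.062)
- removing 30% of each leaves 259, with 130 LS (0.074)
- removing 70% of LS and 50% of non-LS leaves 148, with 56 LS (0.093)

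That is enough to evaluate a model, but it argues against building a separate one there.

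**The case against.** The strongest reply is that the design is sound and the rest belongs to the SAP. Consecutive new referrals give a realistic spectrum for a specialist clinic, and section 3.2 explains the setting by access to the reference standard and feasibility. Section 1.3 also describes a tool for a range of health professionals, not one confined to early or untreated disease. Subgroup reporting is often left to the SAP, nothing in 7.1 forbids it, and the needed fields are collected. All of this stands against any call to exclude women or change the design. It does not remove the point: eligibility, the pooled model and the descriptive role are set in the protocol, and the only stated use of these fields does not serve the stated aim.

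A reader might infer more, in three ways that the documents do not support.

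- *That the weights of reversible signs will be 12% to 47% too small.* This assumes the treated share, treats disease remission as clearance of one sign, and treats only LS women. Section 6.1 records treatment for all participants, and treating both groups alike gives 8% to 29%. Women referred with a continuing complaint may also be those who did not respond.
- *That the specialist's diagnosis is anchored on the earlier label.* No section says so. It is a clinical diagnosis that may include biopsy (3.3.2), and later amendments are recorded (section 8, Adverse Events).
- *That the model should be refitted in untreated women, or judged by its sensitivity in early LS.* The subset may be small, and steroid response would be sparse or unobservable there. Stage is set by the managing clinician and may rest partly on anatomical change, itself a predictor, and sensitivity needs a threshold that 7.1 leaves to patients and doctors.

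**Conclusion.** The point holds as a cheap improvement. Followed as written, section 7.1 yields a C statistic and calibration for a mixture of already-labelled, treated and undiagnosed women, and these need not carry over to the undiagnosed women named in the rationale.

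The real size is unknown, because the share of diagnosed or treated women is not given. On assumed rates the overstatement of the pooled C statistic is small at a 10% share and grows with the share. The effect falls on predictor weights, calibration (modestly, on average, in the simulation) and pooled performance. Ranking within early untreated women hardly moves (C between 0.762 and 0.776). A claim that the tool would fail in early LS is therefore not supported.

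The simulation also treats every previously diagnosed or treated woman as established and every other woman as early. Section 1.3 describes delayed diagnosis, so some undiagnosed women will have late disease, and the true contrast may be weaker.

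**What to change.** In section 7.1, keep eligibility and the pooled model, and add:

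1. The pooled model's C statistic and calibration, with confidence intervals, in women (LS and non-LS alike) with no prior LS diagnosis, and in those who are also not on active treatment. For optimism correction, repeat the whole backward selection on the full dataset in each bootstrap sample and evaluate in the same subgroup. A bootstrap confined to the subgroup would miss optimism from selection on the pooled data.
2. A sensitivity analysis of the model without the steroid-response item.
3. The C statistic for early-stage LS against non-LS, labelled descriptive because of the possible overlap between stage and anatomical predictors.
4. A sentence that claims about first or early diagnosis rest on the results in undiagnosed women, not on the pooled result.

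The cost is a few extra analyses with wider intervals. Every field needed is already on the case report form, and recruitment does not change.
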